#### Notes / definitions:

- AEs will be coded using the MedDRA dictionary version 25.0.
- Adverse Device Effects (ADE) are defined as all AEs recorded in the eCRF with a possible, probable or causal relationship to RGn550.
- ADE occurring during the first session (at D0) are defined as all ADE with a start date equal to the date of D0.
- ADE occurring during the second session (at D7) are defined as all ADE with a start date equal to the date of D7.

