9.5.5.5. Schedule

Table 2 below summarizes procedures and evaluations to perform at each visit.

| | |
|--|--------------|
| 2022.08.11_RGnCON_Prot_Final_V2.0_clean_public | Page 45 / 82 |
|--|--------------|

| | | |
|--------|---|---|
| RGnCON | Clinical Investigation Plan Version 2.0 - 11 August 2022 |  |
|--------|---|---|

Table 2: Schedule of procedures and evaluations

| | D0 | | D7 | | D14 (remote) | D52 |
|--|------------------|-----------------|------------------|-----------------|-----------------|-----|
| | Before treatment | After treatment | Before treatment | After treatment | | |
| Patient information / Informed consent | X | | | | | |
| Eligibility criteria | X | | | | | |
| Pregnancy test for women of childbearing potential | X | | | | | |
| Randomization | X | | | | | |
| Demographic and clinical data | X | | | | | |
| NPC | X | X | X | X | | X |
| Cover test | X | X | X | X | | X |
| Maddox rod test | X | X | X | X | | X |
| Stabilometric test | X | X | X | X | | X |
| TMT A&B | X | | | X | | |
| SCAT5 symptom evaluation tool | X | | X | | X | X |
| Blood sampling | X | | | | | X |
| 20-min treatment session | X | | X | | | |
| Collection of AEs and DDs that previously occurred | | X | X | X | | X |

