### 7.5. Handling of missing data and outliers

#### Handling of missing AE attributes:

AEs with missing relationship, missing seriousness, and/or missing severity will be considered as related to study drug, serious, and severe for the analysis, respectively.

Onset date of AE will be imputed as below. The objective is to maximize the probability the AE is considered as treatment emergent.

Onset date of AE	Imputed AE onset date
Completely missing	Date of first treatment sessions with RGn550
Day is missing	First day of the month.  If imputed date is prior to first treatment sessions with RGn550, then replace with date of first treatment sessions with RGn550.
Day and month are missing	First of January.  If imputed date is prior to first treatment sessions with RGn550, then replace with date of first treatment sessions with RGn550.

End date of AE will not be imputed.

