#### 8.4.4. Adverse device events by MedDRA SOC and MedDRA PT

For all ADEs, a descriptive analysis will be provided by MedDRA SOC and MedDRA PT, by randomization arm and overall.

For all ADEs occurring during the first session (at D0), a descriptive analysis will be provided by MedDRA SOC and MedDRA PT, by randomization arm and overall.

For all ADEs occurring during the second session (at D7), a descriptive analysis will be provided by MedDRA SOC and MedDRA PT, by randomization arm and overall.

The same template as above (i.e. for Adverse events) will be used.

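### The two session ADE tables cover only onsets on the calendar days D0 and D7, and the SAP does not bar imputed onset dates, which would lean towards session 1

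*SAP*

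**What the plan says.** **Session definition.** SAP 6.2.1 (Notes / definitions) gives two parallel rules: "ADE occurring during the first session (at D0) are defined as all ADE with a start date equal to the date of D0" and "ADE occurring during the second session (at D7) are defined as all ADE with a start date equal to the date of D7". It does not say whether the start date is the recorded or the imputed one.

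**Tables that use it.** SAP 8.4.4 plans three ADE tables by SOC and PT: all ADEs with no date limit, first-session ADEs and second-session ADEs. For the last it states: "For all ADEs occurring during the second session (at D7), a descriptive analysis will be provided by MedDRA SOC and MedDRA PT". SAP section 10 lists the two session tables as additions to the protocol.

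**Imputation.** SAP 7.5 replaces a completely missing onset date by "Date of first treatment sessions with RGn550", which is D0. If the day is missing, the date becomes the first of the month; if day and month are missing, 1 January. In both partial cases: "If imputed date is prior to first treatment sessions with RGn550, then replace with date of first treatment sessions with RGn550". The stated purpose is "The objective is to maximize the probability the AE is considered as treatment emergent". AEs with missing relationship, seriousness or severity "will be considered as related to study drug, serious, and severe for the analysis, respectively", so an AE with no recorded relationship becomes an ADE.

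**Collection.** Protocol 9.13.3 records all AEs from inclusion to the end of the 52-day follow-up and names the event date, but no clock time, among the items collected. Protocol Table 2 has a row "Collection of AEs and DDs that previously occurred", marked after treatment at D0, before and after treatment at D7, and at D52.

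**The concern.** A reader will probably use the two tables to compare the first exposure with the second. Two features limit that use.

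First, an ADE that starts the day after a session, even one the investigator judges device-related, is in neither table, and no other planned table relates it to a session.

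Second, the imputation rule was written for treatment emergence, but the AE analyses use all collected AEs and none filters on treatment emergence. The session tables are the only planned ADE analyses in which the onset date matters. (The patient-years alternative applies only if loss to follow-up exceeds 10%, and SAP 8.4.1 reports 0%.) So the rule could act only where it was not designed to act, and there it moves ADEs towards D0. An AE with both relationship and onset date missing would be reported as a first-session ADE.

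There is also a smaller ambiguity. With dates only, an ADE that starts on D7 before the second treatment counts as second-session.

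**Working it through.** **1. The plan's own figure.** Protocol 9.6.1 gives N = 50, ADE probability 0.04 and a 0.87 probability of at least one ADE. 1 − 0.96^50 = 0.870, so it reproduces. Neither this figure nor the primary proportion depends on onset date. The same assumption implies 0.04 × 50 = 2 patients with any ADE in the whole trial, so session counts may be small.

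**2. Days covered.** D0 to D52 is 53 calendar days. The definitions cover 2 (D0 and D7). The remainder is 6 (D1-D6) + 45 (D8-D52) = 51 days, and 51/53 = 96.2%.

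**3. Where an imputed date lands.** Assumptions: every D0 from 1 September to 31 December 2022 (the planned recruitment months, 30 + 31 + 30 + 31 = 122 days) has equal weight, every onset day within a range has equal weight, and D7 and D52 fall exactly 7 and 52 days after D0.

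*Completely missing date:* 100% to D0, whatever the true onset.

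*Day missing, true onset D7:*
- To D0 when D0 and D7 share a month: 23 + 24 + 23 + 24 = 94; 94/122 = 77.0%.
- To D7 only when D7 is the first of a month: 4/122 = 3.3%.
- To neither: 24/122 = 19.7%.

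*Day missing, true onset D8-D52* (122 × 45 = 5,490 combinations):
- To D0 when onset is still in the month of D0: 253 + 276 + 253 + 276 = 1,058; 1,058/5,490 = 19.3%.
- To D7: 30 + 29 + 30 + 30 = 119; 119/5,490 = 2.2%.
- To neither: 4,313/5,490 = 78.6%.

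| Missing part | True onset | To D0 | To D7 | Neither |
|---|---|---|---|---|
| Whole date | any | 100% | 0% | 0% |
| Day | D1-D6 | 88.5% | 0% | 11.5% |
| Day | D7 | 77.0% | 3.3% | 19.7% |
| Day | D8-D52 | 19.3% | 2.2% | 78.6% |
| Day and month | D7 | 94.3% | 0.8% | 4.9% |
| Day and month | D8-D52 | 75.4% | 0.8% | 23.8% |

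A true D0 onset always stays on D0, so imputation never moves an ADE from session 1 to session 2.

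**4. Effect on counts, as a range.** The documents give no number of missing onset dates. Assume 10 ADEs (4 on D0, 4 on D7, 2 later) and a share m with a completely missing date, spread evenly. Session 1 = 4(1 − m) + 10m; session 2 = 4(1 − m); neither = 2(1 − m).

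| m | Session 1 | Session 2 | Neither |
|---|---|---|---|
| 0 | 4 | 4 | 2 |
| 10% | 4.6 | 3.6 | 1.8 |
| 20% | 5.2 | 3.2 | 1.6 |

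At m = 0 there is no distortion. At m = 20%, a true 4:4 split would be shown as 5.2 to 3.2.

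**The case against.** The strongest defence has four parts.

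- **The tables do what their titles say.** They are about ADEs during a session, and same-day onset is a reasonable proxy when only dates are held. The SAP never says that they attribute ADEs to an exposure. This largely stands, and it is why the same-day counts should be kept. It is not complete: a calendar day is wider than a 20-minute session and takes in D7 events from before treatment.
- **Nothing is lost.** A reader might infer that delayed ADEs disappear from the analysis. They do not. They remain in the primary endpoint, the severity endpoints, the all-ADE table and the individual listings. This stands in full.
- **The shift towards session 1 is hypothetical.** A reader might infer that session 1 is inflated. That needs incompletely dated ADEs and use of the imputed date, and the documents establish neither. Reporting within 3 days of awareness, automatic eCRF queries for missing data and a data review before lock all work against missing dates. This stands as a limit on size. It does not remove the silence in SAP 6.2.1.
- **Partial dates do not all go to D0.** Correct: with only the day missing, an onset on D8-D52 lands in neither table in 78.6% of cases.

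A further caution applies to any remedy. Crediting every ADE after D7 to session 2 would rule out delayed effects of session 1 by definition.

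**Conclusion.** The point holds as a minor one, confined to two added descriptive tables. The coverage gap is certain from the text: 51 of 53 recording days feed neither table. The lean towards session 1 is conditional. It arises only if some ADE has an incomplete onset date and the imputed date is used, and it is zero otherwise. Where it arises, imputation takes nothing from session 1. It sends all completely missing dates to D0, and about 77% of true D7 onsets with only the day missing. The percentages for partial dates rest on the planned recruitment months, equal weights and exact visit spacing. The documents do not support saying that delayed ADEs drop out of the safety analysis or that the session 1 count is in fact too high.

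**What to change.** In SAP 6.2.1 and 8.4.4:

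1. State that imputed onset dates are not used for the session tables.
2. Show ADEs without a full onset date by the visit at which they were collected (D0 after treatment, D7 before, D7 after, D52). If that visit cannot be identified, show them as 'session not determinable'.
3. Keep the present counts, labelled 'onset on the calendar day of D0' and 'onset on the calendar day of D7'.
4. Add a row for onset after D0 and before the D7 session, and a row for onset after D7 up to D52. Exclude from the latter any event after the optional session that Protocol 9.5.5.4 allows at D52. A D7-dated ADE already noted at the pre-treatment collection should be counted once, in the between-sessions row, with a footnote.
5. Note under the table that the later-onset rows describe timing and do not show which session caused the event.

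The cost is a few sentences of SAP wording and a few table rows. AE collection is already tied to these visits, so no new data are needed. The primary endpoint, the severity endpoints and their confidence intervals are unaffected.

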#### 6.2.2. Secondary performance endpoints

According to section 9.5.4.2 of the Protocol, the following endpoints will be used to address Secondary performance objectives:

- Automated oculomotor and oculopostural functions will be used as recorded in the eCRF, before and after treatment session at D0 and D7 and then at D52:
  - Convergence, evaluated with the measure of the Near Point of Convergence (NPC)
  - Deviations:
    - Cover test
      - Normal fixation of both eyes
      - Abnormal with at least one eye
    - Maddox rod test:
      - Horizontal deviation (yes/no)
      - Vertical deviation right eye (yes/no)
      - Vertical deviation left eye (yes/no)
- Balance function will be used as recorded in the eCRF, before and after treatment session at D0 and D7 and then at D52:
  - Patient's eyes opened

- Statokinesigram area (mm^2)
- Left distribution (%)
- Right distribution (%)
- Patient's eyes closed
  - Statokinesigram area (mm^2)
  - Left distribution (%)
  - Right distribution (%)
- Rombert quotient (RQ)

The Romberg quotient is the ratio between the statokinesigram area (mm^2) with closed eyes (CE) and the statokinesigram area (mm^2) with opened eyes (OE), it will be calculated as follow :

$$RQ = CE/OE.$$

- Statokinetic distribution index (SKDI)

The stato-kinetic distribution index (SKDI) is the result of the STKG area multiply by the ratio of support distribution it will be calculated as follow:

$$SKDI (\text{mm}^2) = STKG \text{ area } (\text{mm}^2) \times (D/d^*)$$

\*D : Highest distribution value (%)

d : Lowest distribution value (%)

- TMT A&B before treatment session at D0 and after treatment session at D7:
  - TMT – A
    - Time to perform the task will be derived as:  
$$\text{Time to perform the task (in second)} = \text{minutes} * 60 + \text{second.}$$
    - Number of errors (will be used as recorded in the eCRF)
  - TMT –B
    - Time to perform the task will be derived as:  
$$\text{Time to perform the task (in second)} = \text{minutes} * 60 + \text{second.}$$
    - Number of errors (will be used as recorded in the eCRF)
  - TMT – B - A
    - Time to perform the task will be derived as:  
$$\text{Time to perform the task (in second)} = \text{Time to perform the task B} - \text{Time to perform the task A}$$
    - Number of errors will be derived as:  
$$\text{Number of errors} = \text{Number of errors B} - \text{Number of errors A}$$
- Concussion syndrome symptoms (SCAT5) will be used as recorded in the eCRF at D0 before treatment, D7 before treatment, D14 and D52
  - Symptom severity score
  - The total number of symptoms
- Blood markers at D0 before treatment to D52 will be used as recorded in the eCRF
  - Anti-inflammatory cytokines InterLeukin (IL)-1 receptor antagonist, IL-4, IL-6, IL-10, IL-11 and IL-13
  - S100 calcium binding protein B (S100B)

- Glial Fibrillary Acidic Protein (GFAP)
- Ubiquitin C-terminal Hydrolase-L1 (UCH-L1).

## 6.3. Other endpoints and variables

### 6.3.1. Demographic data and other baseline characteristics

The following standard characteristics (gender, Practiced sport leading to investigation concussion, etc.) will be used as recorded in the eCRF:

- Demographic and clinical data
- Concussion History

In addition, the following endpoints will be derived:

- Age (years) = (date of informed consent – date of birth) / 365.25
- BMI (kg/m^2) = weight/ height
- Time since concussion (days) = date of informed consent – date of investigation concussion
- Duration of previous concussion (days) = Recovery date - Onset date

### 6.3.2. Concomitant therapies

Concomitant therapies will be coded with WHO-DD version B3 Sept 2019.

## 7. DATA ANALYSIS CONSIDERATIONS

### 7.1. Statistical software

The statistical analysis will be performed using SAS® VIYA v9.4 (or a more recent version).

### 7.2. Type I error, handling of multiplicity issues and alpha adjustement procedures

The global significance level (type I error rate) is set to  $\alpha = 0.05$ . No adjustment of alpha level will be done.

### 7.3. Centre effect and pooling of centres

This section is not applicable because there is only one center in this trial.

### 7.4. Descriptive analyses of quantitative and qualitative variables

Quantitative variables will be described by: N (number of patients with non-missing data), mean, standard deviation (SD), minimum, maximum, median, first quartile (Q1) and third quartile (Q3).

Categorical variables will be described by frequency and percentage of patients in each category. Percentages will be expressed with one decimal place.

### 7.5. Handling of missing data and outliers

#### Handling of missing AE attributes:

AEs with missing relationship, missing seriousness, and/or missing severity will be considered as related to study drug, serious, and severe for the analysis, respectively.

Onset date of AE will be imputed as below. The objective is to maximize the probability the AE is considered as treatment emergent.

Onset date of AE	Imputed AE onset date
Completely missing	Date of first treatment sessions with RGn550
Day is missing	First day of the month.  If imputed date is prior to first treatment sessions with RGn550, then replace with date of first treatment sessions with RGn550.
Day and month are missing	First of January.  If imputed date is prior to first treatment sessions with RGn550, then replace with date of first treatment sessions with RGn550.

End date of AE will not be imputed.

#### Handling of completely or partially missing dates:

For the date of birth, we collect only the month and year, the day of birth will be replaced by the 1st day of the month.

For completely missing dates of performed visits:

- If DO date is missing, then replace with date of first treatment sessions with RGn550.

- If D7 date is missing, then replace with date of first treatment sessions with RGn550 + 7.
- If D52 date is missing, then replace with date of first treatment sessions with RGn550 + 52.

Other missing data will not be replaced.

## 8. PLANNED STATISTICAL ANALYSES

Please note that templates presented in this section are only examples. The final statistical outputs that will be provided may be slightly different (in terms of style, font size, column size, etc.). These templates have been designed using labels of variables from blank CRF. Label of variables in final statistical outputs may be slightly different from those presented here.

### 8.1. Disposition of patients

The following will be provided by randomization arm and overall:

- Number of screened patients
- Number of eligible patients (patients who met all inclusion criteria and no exclusion criteria)
- Number of treated patients
- Among treated patients:
  - Number of patients who completed the Investigation
  - Number of patients who Withdrawn
  - Number and percentage of patients who performed each visit

The following template will be used.

All N=XX	
Patients screened	XX (100.0%)
Patients eligible	XX (XX.X%)
Patients treated	XX (XX.X%)
Among patients treated:	
Patients who completed the Investigation	XX (XX.X%)
Patients who Withdrawn	XX (XX.X%)
Reason (s) for Withdrawal:	
Consent Withdrawal	XX (XX.X%)
Adverse Event	XX (XX.X%)
Clinical Investigation Plan Deviation	XX (XX.X%)
Lost to Follow-up	XX (XX.X%)
Death	XX (XX.X%)
Other	XX (XX.X%)

In addition, the following data will be provided:

- Date of first patient randomized
- Date of last patient randomized
- Date of last patient out (i.e. last visit performed)
- Study duration (days) = date of last patient last visit - date of first patient randomized

## 8.2. Analysis sets

Frequency and percentage of patients included in each analysis sets defined in Section 5 will be provided.

	Total N=XX
Population SCR [n (%)]	XX (100.0%)
Population FAS [n (%)]	XX (XX.X%)
Group of treatment	
RGn550 5Hz [n (%)]	XX (XX.X%)
RGn550 10Hz [n (%)]	XX (XX.X%)
Analysis subgroups:	
NPC>5 at D0 before treatment [n (%)]	XX (XX.X%)
Maddox rod horizontal deviation at D0 before treatment [n (%)]	XX (XX.X%)
Maddox rod vertical deviation on left eye at D0 before treatment [n (%)]	XX (XX.X%)
Maddox rod vertical deviation on right eye at D0 before treatment [n (%)]	XX (XX.X%)
Maddox rod vertical: at least one deviation (left and/or right eye) at D0 before treatment [n (%)]	XX (XX.X%)
Number of previous concussions	
< 3 [n (%)]	XX (XX.X%)
≥ 3 [n (%)]	XX (XX.X%)

## 8.3. Demographic data and baseline characteristics, including medical history and therapies

Descriptive analyses will be provided for all data listed in section 6.3.1, by randomization arm and overall, on the FAS population.

The following templates will be used.

### 8.3.1. Visit at screening

#### 8.3.1.1. Inclusion criteria

	Total N=xx
Male or female aged at least 18 years old [n (%)]	xx.x (xx.x)
Suffering from a concussion syndrome resulting from a shock that occurred during sport practice less than 72h ago, as confirmed by neurological examination via the Head Injury Assessment - Form 3 (HIA3) tool	xx.x (xx.x)
Affiliated to French social security	xx.x (xx.x)
Who provided a dated and signed informed consent form	xx.x (xx.x)

### 8.3.1.2. Non-inclusion criteria

<same template as above>

### 8.3.1.3. Demographic data

	RGn550 5Hz N=xx	RGn550 10Hz N=xx	Total N=xxx
Age (years) <example of continuous data>			
non-missing	xxx	xxx	xxx
mean (sd)	xx.x (xx.x)	xx.x (xx.x)	xx.x (xx.x)
median	xx.x	xx.x	xx.x
q1;q3	xx.x ; xx.x	xx.x ; xx.x	xx.x ; xx.x
min;max	xx.x ; xx.x	xx.x ; xx.x	xx.x ; xx.x
missing			
Gender [n (%)] <example of categorical data>			
non-missing	xxx	xxx	xxx
Female	xx.x (xx.x)	xx.x (xx.x)	xx.x (xx.x)
Male	xx.x (xx.x)	xx.x (xx.x)	xx.x (xx.x)
missing			

### 8.3.1.4. Concomitant therapies by ATC3 and pharmaceutical substance

ATC3 / Pharmaceutical substance(s)	Group of treatment								
	RGn550 5Hz N=xx			RGn550 10Hz N=xx			Total N=xx		
	Nb TRT	Nb pat	% pat	Nb TRT	Nb pat	% pat	Nb TRT	Nb pat	% pat
ANY TREATMENTS	6	6	3.8	12	10	6.3	18	16	5.1
OTHER ANALGESICS AND ANTIPYRETICS	2	2	1.3	7	7	4.4	9	9	2.9
- Metamizole sodium	1	1	0.6	6	6	3.8	7	7	2.2
- Paracetamol	1	1	0.6	1	1	0.6	2	2	0.6
ANTIINFLAMMATORY AND ANTIRHEUMATIC PRODUCTS, NON-STEROIDS	3	3	1.9	2	2	1.3	5	5	1.6
- Ibuprofen	3	3	1.9	2	2	1.3	5	5	1.6
ADRENERGICS, INHALANTS	.	.	.	1	1	0.6	1	1	0.3
- Salbutamol	.	.	.	1	1	0.6	1	1	0.3
ANTIHISTAMINES FOR SYSTEMIC USE	1	1	0.6	.	.	.	1	1	0.3
- Cetirizine	1	1	0.6	.	.	.	1	1	0.3
DECONGESTANTS AND OTHER NASAL PREPARATIONS FOR TOPICAL USE	.	.	.	1	1	0.6	1	1	0.3
- Betamethasone	.	.	.	1	1	0.6	1	1	0.3
PROPULSIVES	.	.	.	1	1	0.6	1	1	0.3

ATC3 / Pharmaceutical substance(s)	Group of treatment								
	RGn550 5Hz N=xx			RGn550 10Hz N=xx			Total N=xx		
	Nb TRT	Nb pat	% pat	Nb TRT	Nb pat	% pat	Nb TRT	Nb pat	% pat
- Metoclopramide	.	.	.	1	1	0.6	1	1	0.3

## 8.4. Safety analysis

### 8.4.1. Analysis of the primary safety endpoint: proportion of patients with at least one ADE after use of RGn550

The proportion of patients with at least one ADE after use of RGn550 in acute concussion syndrome, either at a frequency of 5 or 10 Hz, will be calculated along with its 95% confidence interval (using exact Clopper-Pearson method). This analysis will be performed on the FAS population, by treatment groups and overall.

The following template will be used.

	RGn550 5Hz N=xx	RGn550 10Hz N=xx	Total N=xx
At least one ADE			
Non-missing	xx	xx	xx
Yes [n (%) 95% CI]	xx (xx.x) xx.x ; xx.x	xx (xx.x) xx.x ; xx.x	xx (xx.x) xx.x ; xx.x
No [n (%) 95% CI]	xx (xx.x) xx.x ; xx.x	xx (xx.x) xx.x ; xx.x	xx (xx.x) xx.x ; xx.x
missing	xx	xx	xx

Note: a lost to follow-up rate of 10% is anticipated. If this rate is higher, an analysis of the primary endpoint using percentage of patient-years will be considered.

Note: at the time of writing this SAP version, a data review has been performed showing that the lost-to-follow-up rate is 0%.

### 8.4.2. Analysis of the secondary safety endpoints / overall summary of adverse events

For all secondary safety endpoints listed in Section 6.2.1, a descriptive analysis will be provided. Table will summarize the number and percentage of patients experiencing the event and the 95% CI. The same analysis will be performed for SAE and SADE.

All AEs collected in the eCRF will be used for the analysis.

The following template will be used.

	RGn550 5Hz N=xx	RGn550 10Hz N=xx	Total (N=XX)
Secondary safety endpoints:			
At least one AE - N (%)	xx (xx.x)	xx (xx.x)	xx (xx.x)
95% CI	xx.x ; xx.x	xx.x ; xx.x	xx.x ; xx.x
At least one ADE - N (%)	xx (xx.x)	xx (xx.x)	xx (xx.x)
95% CI	xx.x ; xx.x	xx.x ; xx.x	xx.x ; xx.x

	RGn550 5Hz N=xx	RGn550 10Hz N=xx	Total (N=XX)
At least one mild ADE - N (%)	xx (xx.x)	xx (xx.x)	xx (xx.x)
95% CI	xx.X ; xx.X	xx.X ; xx.X	xx.X ; xx.X
At least one moderate ADE - N (%)	xx (xx.x)	xx (xx.x)	xx (xx.x)
95% CI	xx.X ; xx.X	xx.X ; xx.X	xx.X ; xx.X
At least one severe ADE - N (%)	xx (xx.x)	xx (xx.x)	xx (xx.x)
95% CI	xx.X ; xx.X	xx.X ; xx.X	xx.X ; xx.X
At least one DD - N (%)	xx (xx.x)	xx (xx.x)	xx (xx.x)
95% CI	xx.X ; xx.X	xx.X ; xx.X	xx.X ; xx.X
Other categories of AEs:			
At least one SAE - N (%)	xx (xx.x)	xx (xx.x)	xx (xx.x)
95% CI	xx.X ; xx.X	xx.X ; xx.X	xx.X ; xx.X
At least one SADE - N (%)	xx (xx.x)	xx (xx.x)	xx (xx.x)
95% CI	xx.X ; xx.X	xx.X ; xx.X	xx.X ; xx.X

